1 PROTOCOL SUMMARY

1.1 SYNOPSIS

Title: A Pilot Phase I/II Study to Evaluate the Safety and Efficacy of TWB-103 in Treating Lower Limb Ulcers on Patients with Diabetes Mellitus

Study Description: This study is designed in a Phase I/II, single-arm manner. This study plans to enroll 10 subjects (for 8 evaluable, per-protocol subjects) with diabetic lower limb ulcers for treating with up to 12 weekly applications of TWB-103 and evaluating the safety and efficacy of TWB-103. TWB-103 will be applied to the target ulcer wound once a week by the investigator, starting from Day 1, until wound closure is confirmed or up to 12 weekly applications. An ulcer wound is considered healed only after closure is confirmed at the visit 2 weeks later. Therefore, a wound closure should be observed at three consecutive visits (i.e. a duration of 2 weeks) for an ulcer to be deemed as healed. Following the confirmation of wound closure or completion of 12-week treatment period, whichever comes first, subjects will start a 24-week follow-up period.

The potential subjects with diabetic lower limb ulcer will be arranged to receive standard of care only for at least 2 weeks during screening period. Any subject whose study ulcer size decreases by at least 30% after this standard of care will be excluded from the study.

If the study ulcer wound is not closed after TWB-103 treatment, standard of care will be applied during the following 24 weeks of follow-up. If the study ulcer wound is healed after TWB-103 treatment, appropriate standard of care should still be applied for protection.

The first 3 subjects will be recruited sequentially with a 3-week staggering in the initiation of study treatment. Patients who experience \geq Grade 1 allergic reaction at least possibly related to the investigational product (section 8.4.3.2), has $>$ Grade 2 skin infection in the ulcer wound, or the treatment for the ulcer wound infection requires subject's hospitalization, intravenous infusion or muscular injection of antibiotics, must not receive any further TWB-103 treatment. Additionally, if major surgery debridement is required, the subject should stop TWB-103 treatment. The study will be stopped when \geq 3 subjects received TWB-103 have developed grade 3 or above AEs according to CTCAE 5.0, independent of attribution. If the cause of AE can be identified and resolved, the study may be resumed.

Objectives: **Primary Objective:** To assess the safety profile of TWB-103 administered to subjects with diabetic lower limb ulcers

Secondary Objective: To explore the efficacy of TWB-103 administered to subjects with diabetic lower limb ulcers

Endpoints: **Primary Endpoint:** Incidence of adverse events (AEs) and serious adverse events (SAEs). Pre-existing abnormalities are considered as AE or SAE only when the conditions escalate. The following events should be discussed

specifically:

1. Study wound and its periphery: Infection, pain, pruritus/irritation, skin dysfunction/blister, osteomyelitis, cellulitis, edema/swelling and unexpected surgery
2. Non-study area and systemic: Infection, pain, pruritus/irritation, skin dysfunction/blister, osteomyelitis, cellulitis, edema/swelling, unexpected surgery, accidental injury, abnormal lab test and general disorders

Secondary Endpoints:

1. The percentage of subjects with confirmed study wound closure at each week up to 12 weeks.
* Wound closure is defined as “full epithelialization of the wound with the absence of drainage or dressing requirement and without sign of abscess under the epithelium”. An ulcer is considered healed only after wound closure is re-confirmed at the visit 2 weeks later. Therefore, a wound closure should be observed at three consecutive visits (i.e. a duration of 2 weeks) for an ulcer to be deemed as healed.
2. Time (days) to confirmed wound closure for those subjects whose wounds are healed during treatment period and during the study period.
3. Reduction of individual wound area for up to 12 weeks.
4. Reduction of wound area at each week up to 12 weeks.
5. General granulation rate and quality of granulation tissue.
6. Reduction of wound volume for individual subject measured by 3D camera and analysis software up to 12 weeks (only for those subjects who have received the 3D measurement).

Study Population:

Ten subjects aged at least 20 years old (inclusive) with diabetic lower limb ulcers presented for at least 4 weeks are planned to enroll in Taiwan.

Inclusion Criteria

In order to be eligible to participate in this study, an individual must meet all of the following criteria:

1. Adults at least 20 years of age.
2. With diagnosed diabetic mellitus (DM), e.g. currently under DM medication treatment, or with $\text{HbA1c} \geq 6.5\%$ but $\leq 12\%$, or with fasting plasma glucose $\geq 126 \text{ mg/dL}$ (7.0 mmol/L), or with plasma glucose $\geq 200 \text{ mg/dL}$ (11.1 mmol/L) in the two-hour 75-gram oral glucose tolerance test (OGTT).
3. With at least one cutaneous ulcer on or below malleoli, and not healing for at least 4 weeks (the ≥ 2 -week standard of care period can be counted as part of the 4-week ulcer history).
4. With ankle brachial index (ABI) ≥ 0.4 on the limb with the study ulcer. For subjects with $0.6 > \text{ABI} \geq 0.4$, the investigator will arrange for providing proper treatment to the subject, such as improving circulation by medication or surgical procedures, etc.
5. The study wound is not prone to infection (the wound can be maintained clean and well bandaged, there is no nearby infected lesion, and there is no history of recurrent infections).
6. The wound should allow complete sealing of the wound by TegadermTM film.
7. The study wound size is between 1~33 cm². The wound depth should be at

least full-thickness ulcer (penetrating skin). The depth of wound may reach ligament, joint capsule, fascia, or tendon. There should be no sign of osteomyelitis. The wound does not exceed Wagner Grade 2⁷.

8. Under the standard care of Investigator for at least 2 weeks, the study wound has not shown significant healing. Significant healing is defined as the following: The area of healed tissue reaches at least 30% of the area of initially presented wound.
9. When the subject has more than one wound which met the inclusion criteria, only one wound is selected as the study wound. The other wounds will be treated by standard cares.
10. Except hyperglycemia, co-morbidities are under control and non-life threatening as determined by the Investigator based on medical history, physical examination, vital signs, or clinical laboratory tests, etc.
11. A negative pregnancy test at Screening. This applies to any female subject with childbearing potential.
12. Agrees to use acceptable contraceptive methods while on study (from signing informed consent form to the end of the study).
Acceptable contraceptive methods include:
 - a. Established use of oral, injected or implanted hormonal methods of contraception
 - b. Placement of an intrauterine device (IUD) or intrauterine system (IUS)
 - c. Barrier methods of contraception: condom or occlusive cap (diaphragm or cervical/vault caps)
13. Able to follow the Investigator's instruction on wound care.
14. With signed informed consent form.

Exclusion Criteria

Any subject meeting any of the exclusion criteria will be excluded from study participation:

1. Being pregnant or nursing.
2. With autoimmune disease other than diabetes, e.g. lupus erythematosus, multiple sclerosis.
3. With current malignancy or hypo-immunity.
4. With history of recurrent cancer, metastatic cancer, cancer which has high probability of metastasis, or cancer on the limb where the study wound is located.
5. With any serum chemistry or hematology abnormalities below
 - a. AST or ALT > 5 × ULN
 - b. Serum albumin < 2.0 g/dL
 - c. Serum creatinine concentration is > 2.5 mg/dL
 - d. WBC is < 2,000/µL
 - e. ANC is < 1,000/µL
 - f. Platelet count is < 100,000/µL
6. With history of HIV infection
7. With history of alcoholism or drug abuse.
8. Received any cell-based product at the study wound.
9. Received an investigational drug, device or biological/bioactive treatment within 30 days prior to Screening Visit.
10. With any clinical condition or significant concurrent disease judged by the investigator to complicate the evaluation of the trial treatment.
11. With history of sensitivity to materials of bovine, porcine origin, or

human serum albumin.
12. With active infection or active osteomyelitis in the study wound.

Phase: I/II

[figure not shown]
Study site: Multiple sites in Taiwan

Study Intervention: TWB-103 (mixture of TWB-102 Cell and TWB-103 Hydrogel, 6×10^5 cells/ml). TWB-102 Cell is live human fetal dermal fibroblast. The dosage used in this study is 0.15 ml TWB-103/cm² of ulcer area.

Study Duration: Approximately 18 months

Participant Duration: Approximately 10 months

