Apligraf® is an allogeneic bio-engineered skin equivalent that contains an upper epidermal layer and a lower dermal layer. The epidermal layer is formed by cultured human foreskin-derived neonatal keratinocytes while the dermal layer is formed by cultured human foreskin-derived fibroblasts growing in bovine type I collagen matrix. Therefore, Apligraf® mimics the normal skin. In the study of Apligraf® for diabetic foot ulcer, 208 patients were randomly assigned to either with Apligraf® (112 patients) or saline-moistened gauze (96 patients, control group)⁶. Patients had up to 5 weekly application of Apligraf® and were followed for 12 weeks. The results showed that 63 (56%) Apligraf®-treated patients achieved complete wound healing compared with 36 (38%) in the control group ($P = 0.0042$) during the 12-week follow-up period. The median time to complete closure were 65 days and 90 days for Apligraf®-treated group and control group, respectively.

From the experience above, using fibroblasts to treat diabetic foot ulcers is feasible and also effective. TWB-103, developed by Transwell Biotech Co., Ltd., is a mixture of TWB-102 cell and TWB-103 hydrogel. TWB-102 cell contains live human fetal dermal fibroblasts (FE002-SK2 cells). In the current clinical trial for treating donor site wound, to each cm^2 of wound about 4 μL of TWB-102 cell product (which contains 30,000 FE002-SK2 cells) is applied. The hydrogel is used to dilute and stabilize cells and confine the cells within targeted wound area without disturbance to the therapeutic functions of the cells. The safety and efficacy of TWB-103 are tested in the following studies.

Non-Clinical Experience

Effect of the cellular components of TWB-103 on the migration of primary human keratinocytes

It is well established that TWB-102 cells stimulate keratinocyte migration in a co-culture system. Assay for such effect of TWB-102 cells is routinely conducted as a part of product release testing of TWB-102 cells.

Effect of the cellular components of TWB-103 on the proliferation of primary human keratinocytes

Three studies indicated that live TWB-102 cells, killed/broken TWB-102 cells and mitomycin C-treated FE002-SK2 cells were all capable of stimulating keratinocyte proliferation.

Semi-quantitative array profiling of TWB-102 cell

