4 STUDY DESIGN

4.1 OVERALL DESIGN

This study is to evaluate if applying TWB-103 on diabetic ulcer wound can speed up the wound healing in subjects with diabetic lower limb ulcer which has not shown healing for at least 4-week duration. This study is designed in a Phase I/II, single-arm manner. This study plans to enroll 10 subjects (including 8 evaluable per-protocol subjects) with diabetic lower limb ulcers for treating with up to 12 weekly applications of TWB-103 and evaluating the safety and efficacy.

Eligibility will be checked during screening and at Day 1 Visit. The potential subjects with diabetic lower limb ulcer will be arranged to receive standard of care only for at least 2 weeks during screening period. The standard of care will be performed at the investigator's discretion based on the condition of each subject. Any subject whose study ulcer size decreases by 30% or more after this standard of care will be excluded from the study.

TWB-103 is applied once a week by the investigator at the study site, starting from Day 1, until wound closure is confirmed or up to 12 weekly applications. An ulcer is considered healed only after closure is confirmed at the visit 2 weeks later. Therefore, a wound closure should be observed at three consecutive visits (i.e. a duration of 2 weeks) for an ulcer to be deemed as healed. For wound closure which is first observed at Week 11 or Week 12, and has a confirmation at Week 13 or Week 14, respectively, will be considered as a healed wound closure within 12 weeks. If any subject has confirmed wound closure before week 12, he/she will stop TWB-103 application and complete assessments of End-of-Treatment (Week 12).

Following the confirmation of wound closure or completion of 12-week treatment period, whichever comes first, subjects will start a 24-week follow-up period. Subjects will have follow-up visits at weeks 13, 14, 16, 20, 24, 30 and 36, if the 12-week treatment period is completed. Those subjects who have confirmed wound closure before week 12 will have follow-up visits at 1 week, 2 weeks, 4 weeks, 8 weeks, 12 weeks, 18 weeks and 24 weeks after the End-of-Treatment Visit.

If the study wound is not closed after TWB-103 treatment, standard of care will be applied during the following 24 weeks of follow-up. If the study wound is healed after TWB-103 treatment, appropriate standard of care should still be applied for protection.

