9.3 POPULATIONS FOR ANALYSES

The following populations will be introduced for statistical analysis.

Intend-to-treat (ITT) population:

- All enrolled subjects who have received at least one application of TWB-103
- With any post-treatment evaluation

Per-protocol (PP) population:

- A subset of ITT population
- Fulfill all inclusion and exclusion criteria
- Dosed with at least 9 applications of TWB-103, OR with early confirmed wound closure and at least 75% treatment application
- With efficacy endpoint measurement at wound assessment
- Not received any prohibited treatment during TWB-103 treatment period

Safety evaluations will be performed on ITT population. Analysis of efficacy endpoints will be performed on ITT and PP population. The main conclusion will be made on ITT population analysis results of the primary endpoint.

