9.4 STATISTICAL ANALYSES

9.4.1 GENERAL APPROACH

There will be a separate formal statistical analysis plan (SAP) to be completed prior to database/data lock. The SAP generally includes additional statistical analysis detail (e.g., more detail of analysis populations, summary of statistical strategies). Any deviations from the planned analysis as described in the SAP will be justified and recorded in the final clinical study report.

The baseline value of each assessment will be the value assessed closest and prior to 1st application of TWB-103.

Descriptive statistics will be provided for all endpoints.

Continuous variables will be summarized by reporting the number of observations, mean, standard deviation, median, interquartile range (IQR = third quartile (Q3) - first quartile (Q1)), Q1, Q3, minimum and maximum.

Categorical variables will be summarized using frequency tables showing the number and percentage of subjects within a particular category.

Ordinal endpoints will be presented by transition tables.

Healing time from baseline to wound closure will be estimated by using Kaplan-Meier method.

The data changes from baseline value will be analyzed by one-sample t-test or Wilcoxon sign rank test. The baseline value of each assessment will be the value assessed closest and prior to 1st application of TWB-103. The Last Observation Carried Forward (LOCF) method will be applied for dealing missing data of the efficacy endpoints.

All comparisons will be conducted with significance level of 0.05, using 2-tailed tests where 95% confidence interval for difference and corresponding *p*-value will be presented.

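### Time to confirmed closure is defined only for subjects who heal, has no censoring rule, and relies on a confirmation rule whose two forms disagree after Week 12

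*Combined protocol and SAP*

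**What the plan says.** Sections 1.1 and 3 list secondary endpoint 2 as "Time (days) to confirmed wound closure for those subjects whose wounds are healed during treatment period and during the study period". It therefore covers both the treatment period and the whole study, but only subjects who heal.

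On analysis, section 9.3 states: "Analysis of efficacy endpoints will be performed on ITT and PP population". Section 9.4.1 states: "Healing time from baseline to wound closure will be estimated by using Kaplan-Meier method", and also: "Descriptive statistics will be provided for all endpoints". No cut-off or censoring rule is given for the curve. The only missing-data rule for efficacy is LOCF, which is not a censoring rule. Section 9.4.3, on the secondary endpoints, does not mention time to closure. Section 9.4.1 defers further detail to a separate SAP, which is not part of the text reviewed.

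Confirmation is stated in two forms in section 1.1. The first is "An ulcer is considered healed only after wound closure is re-confirmed at the visit 2 weeks later". The second is "a wound closure should be observed at three consecutive visits (i.e. a duration of 2 weeks) for an ulcer to be deemed as healed". Section 4.1 adds a provision for closure "first observed at Week 11 or Week 12, and has a confirmation at Week 13 or Week 14, respectively", and nothing for closures first seen later. The follow-up visits are at Weeks 13, 14, 16, 20, 24, 30 and 36.

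**The concern.** **Population and censoring.** Restricting a time-to-event endpoint to those who have the event conditions on the outcome. With no censored subjects, a Kaplan-Meier curve is simply the distribution of healing days among healers. It falls to zero unhealed however few subjects heal, and it produces a median whenever anyone heals. A reader would take that median as the healing time of treated subjects.

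Section 2.2 makes a misreading more likely. It reports for another cell product and its control: "The median time to complete closure were 65 days and 90 days". The 90 days belongs to a control arm with 38% healed in a 12-week (84-day) follow-up. Visit windows aside, it cannot be a median among those healed in that window. A healers-only median from this trial would be on a different basis and would look faster beside it.

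**Confirmation.** Endpoint 2 runs to the end of the study, and section 4.2 gives further assessment of healing as one purpose of follow-up. After Week 12 it is the only closure endpoint. If the two forms of the rule disagree there, the same wound can be counted as healed or not healed.

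**Working it through.** **1. The plan's own figure: three consecutive visits equal 2 weeks.** Inputs are the target days and windows in section 1.3: Day 1 + 7 × week (±2) up to Week 12, then Days 92 and 99 (±2), 113 (±3), and 141, 169, 211 and 253 (±6). The span is the day of the third visit minus the day of the first. The range adds or subtracts both windows.

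| Closure first seen | Span of three visits, days (window range) | Scheduled visit exactly 2 weeks later? | First scheduled visit at least 14 days later |
|---|---|---|---|
| Weeks 1–12 | 14 (10–18) | Yes | 14 days |
| Week 13 | 113 − 92 = 21 (16–26) | No | Week 16, 21 days |
| Week 14 | 141 − 99 = 42 (34–50) | Yes, Week 16 | Week 16, 14 days |
| Week 16 | 169 − 113 = 56 (47–65) | No | Week 20, 28 days |
| Week 20 | 211 − 141 = 70 (58–82) | No | Week 24, 28 days |
| Week 24 | 253 − 169 = 84 (72–96) | No | Week 30, 42 days |
| Week 30 | Not available | No | Week 36, 42 days |
| Week 36 | Not available | No | None |

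The figure reproduces through Week 12 and fails at every follow-up visit. The windows do not rescue it, since the shortest possible span after Week 12 is 16 days. Of the 7 follow-up visits, a first closure can be confirmed by scheduled visits at 1 (a visit exactly 2 weeks later), 5 (three visits) or 6 (a visit at least 2 weeks later). A wound closed at Weeks 14 and 16 but reopened by Week 20 is healed under the first form and not healed under the second.

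**2. Healers-only against all-subject curve, n = 10.** The event days are assumed, non-healers are censored at Day 253, and the median is the first day on which the curve is at or below 0.5.

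- Three heal (Days 36, 57, 78). Healers only: the curve reaches 0 and the median is Day 57. All ten: the curve stops at 0.70 and the median is not reached.
- Six heal (Days 29, 36, 50, 57, 71, 78). Healers only: median Day 50. All ten: median Day 71.

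**3. Size from the cited figures, without a hazard model.** Section 2.2 gives 63/112 = 56.25% healed in 12 weeks and a median of 65 days. If 65 days is an all-subject median and 56.25% is the curve's value at 84 days, day 65 is the 0.50/0.5625 = 89th percentile of the healers' own times. Their median then lies before day 65.

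**4. Constant-hazard illustration.** Assume 12-week shares p = 0.30 (39/130) and 0.5625, both from section 2.2. Then λ = −ln(1 − p)/84, the all-subject median is ln 2/λ, and the healers-only median over T days is −ln(1 − F/2)/λ with F = 1 − exp(−λT).

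| | p = 0.30 | p = 0.5625 |
|---|---|---|
| All-subject median | 163.2 days | 70.4 days |
| Healers only, T = 84 | 38.3 days (ratio 4.3) | 33.6 days (ratio 2.1) |
| Healers only, T = 252 | 93.8 days (ratio 1.7) | 62.3 days (ratio 1.1) |
| Chance that at least 5 of 10 heal by Week 12 | 0.15 | 0.76 |

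The last row is a binomial tail and gives the chance that an all-subject median is reached by Week 12 when nobody is censored earlier. As a check on the model, it gives 70 days where section 2.2 reports 65. For the control arm (36/96 = 0.375) it gives 124 days where 90 is reported. It shows direction and rough size only.

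**The case against.** The strongest reply is that Kaplan-Meier exists for censored data and that section 9.3 already places efficacy on ITT and PP, so an all-subject curve is the natural reading. The healers-only wording would then be a descriptive summary alongside it, and the missing censoring rule is a detail for the separate SAP. This reading is possible, but the protocol does not state it. It would still need a censoring rule, and the listed endpoint would remain the healers-only time.

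Several points about size also stand. No passage plans a comparison with the 65- and 90-day medians, so the risk is misreading rather than a faulty planned test. The 89th percentile treats a crude share and a median as points on one curve; if the curve at day 84 were 60% or 70% (assumed), it would be the 83rd (0.50/0.60) or 71st (0.50/0.70) percentile. The direction survives, but the distance below 65 days is not established. The constant-hazard model fits the control arm poorly, and the 36-week figures carry the treatment-period hazard past the end of TWB-103.

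On confirmation, only first closures after Week 12 are affected, possibly none among 10 subjects. Unscheduled ulcer evaluations could supply a 2-week check, but they are at the investigator's discretion. Week 36 is a gap under both forms rather than a disagreement.

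**Conclusion.** The concern holds and should be fixed. As written, endpoint 2 conditions on healing, and the planned Kaplan-Meier estimate has no stated population or censoring rule of its own. A healers-only median is too short for treated subjects: about half the all-subject value or less at 12 weeks in the illustration, with a much smaller gap over 36 weeks when most subjects heal. Those ratios rest on a constant hazard and on healing shares borrowed from other products; the direction does not.

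The disagreement in the confirmation rule rests only on the protocol's own visit days and is certain for closures first seen after Week 12.

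The reach is limited: a secondary, exploratory endpoint in a 10-subject single-arm pilot without hypotheses. The primary safety endpoint and secondary endpoint 1 are unaffected. The separate SAP may already settle the censoring question, but the endpoint definition sits in the protocol.

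**What to change.** - **Endpoint.** Define it for all ITT subjects, repeated in PP, as days from Day 1 to the first visit of a closure that is later confirmed. This matches the dating implied by the Week 8 example in section 8.1.1.
- **Analysis.** Use Kaplan-Meier, with unhealed subjects censored at their last wound assessment. Report to Week 12 and to end of study. Give healers' times as a labelled listing only.
- **Withdrawals.** Those listed in section 7.2 for infection, allergy or major debridement may be informative. Add a sensitivity analysis that keeps withdrawn subjects at risk as unhealed to the end of the window.
- **LOCF.** State that it does not impute closure for confirmation, consistent with section 8.1.1.
- **Confirmation after Week 12.** Reconcile the two forms into one analysis rule before lock, covering Weeks 30 and 36, and say whether unscheduled evaluations count. One option is closure at every scheduled visit up to and including the first at least 14 nominal days later. It equals the present rule through Week 12, needs 2 to 6 weeks of closure afterwards, and leaves only Week 36 unconfirmable by scheduled visits. The three-visit form needs 3 to 12 weeks and leaves Weeks 30 and 36 unconfirmable. The choice is the sponsor's.

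The cost is wording in sections 1.1, 3, 8.1.1 and 9.4.1 and in the SAP, with no new visits or data. The median will be longer or not reached, and some late closures will stay unconfirmed. Censoring at withdrawal does not guarantee an unbiased estimate. For example, suppose 2 of 10 withdraw before any closure and 4 of the other 8 heal by Week 12 (assumed numbers). Censoring gives 4/8 = 50% healed and a median that is reached; keeping the two at risk gives 4/10 = 40% and a median that is not.
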